C _{trough}	single-dose end of dosing interval (trough) concentration
CV	coefficient of variation
CYP	cytochrome P ₄₅₀
DDI	drug-drug interaction
DLT	dose-limiting toxicity
DME	drug metabolizing enzymes
DNA	deoxyribonucleic acid
ECG	Electrocardiogram
ECOG	Eastern Cooperative Oncology Group
eCRF	electronic case report form
EDC	electronic data capture
ELISA	enzyme-linked immunosorbent assay
EOS	End of Study (visit)
EOT	End of Treatment (visit)
EU	European Union
FDA	United States Food and Drug Administration
GCP	Good Clinical Practice
G-CSF	granulocyte colony stimulating factor
GGT	gamma glutamyl transferase
GI	Gastrointestinal
GLP	Good Laboratory Practices
GM-CSF	granulocyte macrophage-colony stimulating factor
GMP	Good Manufacturing Practice
Hb	Hemoglobin
Hct	Hematocrit
HDPE	high-density polyethylene
hERG	human ether-à-go-go related gene
HIV	human immunodeficiency virus

CONFIDENTIAL

This document is confidential. Do not disclose or use except as authorized.

Abbreviation	Term
HNSTD	highest nonseverely toxic dose
IB	Investigator's Brochure
IC ₅₀	concentration producing 50% inhibition
ICF	informed consent form
ICH	International Conference on Harmonisation
IEC	independent ethics committee
IRB	institutional review board
ITT	intent-to-treat
IV	intravenous; intravenously
IVRS	interactive voice response system
K _i	inhibition constant
KPS	Karnofsky Performance Status
LDH	lactate dehydrogenase
LFT	liver function test(s)
MedDRA	Medical Dictionary for Regulatory Activities
Millennium	Millennium Pharmaceuticals, Inc., and its affiliates
MRI	magnetic resonance imaging
MRU	medical resource utilization
MTD	maximum tolerated dose
MUGA	multiple gated acquisition (scan)
NCCN	National Comprehensive Cancer Network
NCI	National Cancer Institute
NCI CTCAE	National Cancer Institute Common Terminology Criteria for Adverse Events
NPO	nothing by mouth
NYHA	New York Heart Association
PBMC	peripheral blood mononuclear cell
PCR	polymerase chain reaction
PD	progressive disease (disease progression)
Pgp	P-glycoprotein
PK	pharmacokinetic(s)
PO	per os ; by mouth (orally)
PR	partial response
PRO	patient-reported outcome
PSA	prostate-specific antigen

CONFIDENTIAL

This document is confidential. Do not disclose or use except as authorized.

Abbreviation	Term
QD	quaque die ; each day; once daily
QID	quater in die ; 4 times a day
QOD	quaque altera die ; every other day
QOL	quality of life
QTc	rate-corrected QT interval (millisec) of electrocardiograph
RBC	red blood cell
RECIST	Response Evaluation Criteria in Solid Tumors
SAE	serious adverse event
SC	Subcutaneous
SD	stable disease
SmPC	Summary of Product Characteristics
$t_{1/2}$	terminal disposition half-life
TGI	tumor growth inhibition
T_{\max}	single-dose time to reach maximum (peak) concentration
UK	United Kingdom
ULN	upper limit of the normal range
US	United States
V_z	volume of distribution in the terminal phase
WBC	white blood cell
WHO	World Health Organization

CONFIDENTIAL

This document is confidential. Do not disclose or use except as authorized.

PROTOCOL SUMMARY

Study Title: Phase II Trial of the PD-1 Antibody Nivolumab in Combination with Lenalidomide and Low Dose Dexamethasone in Patients with High-Risk Smoldering Multiple Myeloma	
Phase: II	
Number of Patients: 41	
Study Objectives: Primary Objectives To determine the proportion of high risk smoldering multiple myeloma patients who are progression free at 2 years after receiving Nivolumab and lenalidomide+ dexamethasone combination therapy	
Secondary Objectives 
• To assess the response rate of the combination in these patients• To assess time to progression and progression free survival• To assess duration of response• To assess the safety of the combination• To examine molecular evolution of the tumor cells• To determine the role of immune cells in the progression of smoldering MM• To determine minimal residual disease (MRD)	
Overview of Study Design: This is a single arm phase II study using the combination of Nivolumab and lenalidomide + low dose dexamethasone in patients with high risk smoldering multiple myeloma. The study is designed to examine novel therapeutic immunotherapy combinations in patients with smoldering MM. The trial will include a safety run in of 10 patients. If three of the ten patients experience a serious, unexpected adverse event during their first cycle of therapy, the study will be suspended temporarily until further safety review.	
Study Population: SELECT INCLUSION CRITERIA 
• Age \geq 18 years.• Must meet criteria of high risk smoldering MM as described with one of the below criteria:
○ Bone marrow clonal plasma cells \geq 10% and any one or more of the following:
▪ Serum M protein \geq 3.0g/dL▪ IgA SMM▪ Immunoparesis with reduction of two uninvolved immunoglobulin isotypes▪ Serum involved/uninvolved free light chain ratio \geq 8 (but less than	

CONFIDENTIAL

This document is confidential. Do not disclose or use except as authorized.

100)

- Progressive increase in M protein level (Evolving type of SMM)†
- Bone marrow clonal plasma cells 50-60%
- Abnormal plasma cell immunophenotype ($\geq 95\%$ of bone marrow plasma cells are clonal) and reduction of one or more uninvolved immunoglobulin isotypes

* All patients should have four or six color flow cytometry performed on the baseline bone marrow sample, as feasible. Patients evaluated for eligibility by Spanish Criteria must have their result confirmed by four color flow cytometry. If four or six color flow cytometry is not available at the site, the baseline bone marrow must be sent to Dana-Farber Cancer Institute to confirm eligibility prior to enrollment.

- High risk cytogenetics or FISH including t (4;14) or del 17p or 1q gain
- Increased circulating plasma cells
- MRI with diffuse abnormalities or 1 focal lesion
- PET-CT with focal lesion with increased uptake without underlying osteolytic bone destruction

† Increase in serum monoclonal protein by $\geq 10\%$ on two successive evaluations within a 6 month period

- No evidence of CRAB criteria* or new criteria of active MM which including the following:
 - Increased calcium levels (corrected serum calcium >0.25 mmol/dL {1mg/dL} above the upper limit of normal or >2.75 mmol/dL {11mg/dL});
 - Renal insufficiency (attributable to myeloma);
 - Anemia (Hb 2g/dL below the lower limit of normal or <10 g/dL);
 - Bone lesions (lytic lesions or generalized osteoporosis with compression fractures)
 - No evidence of the following new criteria for active MM including the following: Bone marrow plasma cells $\geq 60\%$, Serum involved/uninvolved FLC ratio $\geq 100^*$, and MRI with more than one focal lesion (*except for light chain smoldering MM)

* Participants with CRAB criteria that are attributable to conditions other than the disease under study may be eligible

- ECOG Performance Status (PS) 0, 1, or 2.
- The following laboratory values obtained ≤ 21 days prior to registration:
 - ANC $\geq 1000/\mu\text{L}$
 - PLT $\geq 50,000/\mu\text{L}$
 - Total bilirubin ≤ 1.5 mg/dL (If total is elevated check direct and if normal patient is eligible.)
 - AST $\leq 3 \times$ institutional upper limit of normal (ULN)
 - ALT $\leq 3 \times$ institutional upper limit of normal (ULN)

CONFIDENTIAL

This document is confidential. Do not disclose or use except as authorized.

SELECT EXCLUSION CRITERIA

- Symptomatic Multiple Myeloma or any evidence of CRAB criteria. Any prior therapy for Multiple Myeloma should also be excluded. Bisphosphonates are not excluded. Patients who received prior therapy due to being incorrectly diagnosed as having overt multiple myeloma may not be excluded after discussion with the overall PI.
- Other concurrent chemotherapy, immunotherapy, radiotherapy, or any ancillary therapy considered investigational. Prior therapy with bisphosphonate is allowed. Prior radiation therapy to a solitary plasmacytoma is allowed.
- Autoimmune disease: Patients with a history of inflammatory bowel disease, including ulcerative colitis and Crohn's Disease, are excluded from this study, as are patients with a history of symptomatic disease (eg, rheumatoid arthritis, systemic progressive sclerosis [scleroderma], systemic lupus erythematosus, autoimmune pneumonitis, autoimmune vasculitis [eg, Wegener's Granulomatosis]) and motor neuropathy considered of autoimmune origin (e.g. Guillain-Barre Syndrome and Myasthenia, Gravis). Patients with Hashimoto's thyroiditis are eligible to go on study. The Overall PI must be consulted to discuss any other autoimmune disorders not listed here to determine if the patient is eligible for the trial.

Duration of Study: 5 years

CONFIDENTIAL

This document is confidential. Do not disclose or use except as authorized.

1. OBJECTIVES

Smoldering Multiple Myeloma (SMM) is a heterogeneous disease entity that includes patients who have a disease burden that is higher than that in patients with MGUS but who are not yet symptomatic¹. The term SMM was first described by Greipp and Kyle et al in 1980² and was followed by many other descriptions terming it indolent MM³, or Durie Salmon Stage I⁴. It was not until 2003 that the International Myeloma Working Group (IMWG) described the exact definition of this disease. SMM was defined as serum M-protein ≥ 3 g/L and/or $\geq 10\%$ monoclonal plasma cells in the bone marrow (BM), Table 1^{5,6}. While the incidence and prevalence of SMM in the population is not well defined, it has been estimated to represent approximately 8% to 20% of patients within the MM spectrum¹.

Most recently, the IMWG further re-defined the group of patients who meet criteria for treatment and included asymptomatic SMM patients who are likely going to have end-organ damage in the near future, previously defined as “ultra-high risk smoldering myeloma”. These include patients with bone marrow plasmacytosis $\geq 60\%$ ⁷; an abnormal FLC-ratio ≥ 100 (involved kappa) or <0.01 (involved lambda)⁸; and/or 2 or more focal bone marrow lesions detected by functional imaging including PET-CT and/or MRI^{9,10}. These patients should therefore not be considered SMM anymore but rather re-defined as patients with myeloma-defining events that require therapy.

The overall risk of progression of SMM is 10% per year for the first 5 years and 3% per year for the next 5 years¹¹. The most common factors used to stratify patients with SMM are the Mayo Clinic criteria^{11,12} and the Spanish PETHEMA criteria¹³. The Mayo Clinic criteria are based on the tumor burden defined by the serum protein level (by serum protein electrophoresis or light chain ratio) or by the percent bone marrow plasma cell involvement (see Table 2)^{11,12}, leading to risks of progression at 5 years of 25% for low risk, 51% for intermediate risk and 76% for high risk individuals who have 1, 2 or 3 risk factors respectively^{11,12}. The risk stratification of the PETHEMA group is based on identifying the number of clonal plasma cells in the bone marrow by flow cytometry ($\geq 95\%$ ratio of abnormal neoplastic plasma cells to normal plasma cells) and reduction of uninvolved immunoglobulins, with 5 year-risk of progression being 4%, 46%, and 72% for patients with 0, 1 or 2 risk factors, respectively¹³.

The paradigm of therapy in Smoldering Multiple Myeloma (SMM) is changing as we develop better therapeutic agents that prevent end organ damage and improve survival of patients with multiple myeloma (MM)¹⁴⁻¹⁶. Indeed, recent studies of a phase III trial of lenalidomide and dexamethasone versus placebo showed improved response, progression free survival and overall survival in patients with high risk smoldering MM compared to placebo control¹⁷. Therefore, there is a need to examine novel therapeutic combinations in patients with high risk smoldering MM.

Our overarching hypothesis is that early therapeutic interventions in patients with smoldering MM will prevent/delay progression to overt MM. We will examine the *in vivo* activity and safety of nivolumab and lenalidomide in patients with high-risk SMM.

CONFIDENTIAL

This document is confidential. Do not disclose or use except as authorized.

1.1 Study Design

This is a phase II study using the combination of Nivolumab and lenalidomide + low dose dexamethasone in patients with high-risk smoldering multiple myeloma. The trial will include a safety run in of 10 patients. If three of the ten patients experience a serious, unexpected adverse event during their first cycle of therapy, the study will be suspended temporarily until further safety review. If any one of the study medications is permanently discontinued for any reason including toxicity, or FDA mandate, the patient may remain on the study at the discretion of the principal investigator.

** As of September 2017, the trial has been put on partial clinical hold by the Food and Drug Administration: all patients are to discontinue nivolumab indefinitely, and no additional patients will be accrued to the trial. Participants may elect to remain on lenalidomide/dexamethasone or lenalidomide therapy alone for disease control after discussion with the overall PI.

1.2 Number of Patients

A total of 41 patients will be included on this study. Enrollment includes patients who receive the first day of therapy.

1.3 Duration of Study

A treatment cycle is defined as 28 consecutive days.

Patients will receive 6 cycles of induction therapy followed by 6 cycles of maintenance therapy with lower doses of lenalidomide and no dexamethasone for a total of 12 months.

During maintenance, if a patient experiences biochemical progression ($\geq 25\%$ increase and an absolute increase of $\geq 0.5\text{g/dL}$ from their nadir in their serum or urine m-spike or FLC with no CRAB features attributable to MM progression) high-dose dexamethasone may be re-added to the combination at a dose of 40mg oral given on days 1, 8, and 15 of a 28 day cycle after discussion with the overall PI.

For all treatment cycles a $+\text{-} 7$ day window is allowed for Nivolumab. For hold and delay guidelines for lenalidomide and dexamethasone, please refer to Table 17. The treatment plan is designed to be administered on an outpatient basis, however if necessary, may be given as inpatient.

Patients will be followed for up to three years after discontinuation of therapy.

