3. PARTICIPANT SELECTION

3.1 Eligibility Criteria

3.1.1 Age \geq 18 years.

3.1.2 Must meet criteria of high risk smoldering MM based on the criteria described below:

Definition of high-risk SMM:

- Bone marrow clonal plasma cells \geq 10% and \leq 60% **and any one or more of the following:**
 - Serum M protein \geq 3.0g/dL (IgA, IgG, IgM, or IgD)
 - IgA SMM
 - Immunoparesis with reduction of two uninvolved immunoglobulin isotypes
 - Serum involved/uninvolved free light chain ratio \geq 8 (but

CONFIDENTIAL

This document is confidential. Do not disclose or use except as authorized.

less than 100)

- Free Light Chain Smoldering Myeloma patients as defined in section 2.4 are not excluded
- Progressive increase in M protein level (Evolving type of SMM)
 - Increase in serum monoclonal protein by $\geq 10\%$ on two successive evaluations within a 6 month period
- Bone marrow clonal plasma cells 50-60%
- Abnormal plasma cell immunophenotype ($\geq 95\%$ of bone marrow plasma cells are clonal) and reduction of one or more uninvolved immunoglobulin isotypes
- t (4;14) or del 17p or 1q gain
- Increased circulating plasma cells
- MRI with diffuse abnormalities or 1 focal lesion
- PET-CT with one focal lesion with increased uptake without underlying osteolytic bone destruction
- Urine monoclonal light chain excretion ≥ 500 mg/24 hours

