11. MEASUREMENT OF EFFECT

11.1 Development of symptomatic disease

In this study, the final endpoint is development of symptomatic MM that requires therapy.

This is defined as one of the following criteria (≥ 1 CRAB Criterion and Myeloma Defining Events ≥ 1 MDE):

- Increased calcium levels (corrected serum calcium >0.25 mmol/dL above the upper limit of normal or >2.75 mmol/dL) due to myeloma
- Renal insufficiency (attributable to myeloma);
- Anemia (Hb 2g/dL below the lower limit of normal or <10 g/dL) due to myeloma
- Bone lesions (lytic lesions or generalized osteoporosis with compression fractures)
- Myeloma Defining Events (MDE) as follows:
 - Clonal bone marrow plasma cell percentage $\geq 60\%$ ⁷
 - An abnormal FLC-ratio ≥ 100 (involved kappa) or <0.01 (involved lambda)⁸
 - 2 or more focal lesions on MRI or PET-CT studies^{9,10}

For measurement of response:

The disease response will be assessed using criteria based on the International Myeloma Working Group Uniform Response Criteria in Section 11.2.2.1 or FreeLite™ Disease Response Criteria in Section 11.2.2.2.

Disease response by the Modified EBMT Response Criteria in Section 11.3.2.3 will also be collected on participants as a secondary measure.

The same method of assessment and technique should be used for disease measurement at baseline and during follow-up. Disease response should be confirmed by two consecutive assessments.

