Stable Disease (SD)	Not meeting criteria for CR, VGPR, PR or progressive disease. This is not recommended as an indicator of response; stability of disease is best described by providing the time to progression estimates.
Progressive Disease (PD)	$> 25\%$ increase of serum M-protein (which must also be an absolute increase of ≥ 0.5 g/dL) and/or urine M-protein (which must also be an absolute increase of ≥ 200 mg/24hr). If serum and urine M-protein are unmeasurable, there must be an absolute increase of ≥ 10 mg/dL between involved and uninvolved FLC levels. PD is also measured by an absolute increase in bone marrow plasma cells $\geq 10\%$. In addition to the above listed criteria, progression may also be measured by a definite development of new bone lesions or soft tissue plasmacytomas or definite increase in the size of existing bone lesions or soft tissue plasmacytomas or development of hypercalcemia (corrected serum calcium ≥ 11.5 mg/dL or 2.65 mmol/L) that can be attributed solely to the plasma cell proliferative disorder.

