11.2.2.2 FreeLite™ Disease Response Criteria

Response	Criteria for Response
Complete Response (CR)	For those patients being followed by serum free light chain (and NO measurable serum or urine M-spike), which were immunofixation negative at enrollment, normalization of serum free light chain ratio. Normalization is defined as the serum free light chain ratio being within the normal range. If the serum free light chain ratio is not within the normal range, but the individual kappa and lambda light chain values are within normal range, this may be considered CR.

Partial Response (PR)	If only measurable parameter is serum immunoglobulins free light chain (FLC), EITHER
------------------------------	---

CONFIDENTIAL

This document is confidential. Do not disclose or use except as authorized.

	
of the following changes qualify as partial response:
 
• $\geq 50\%$ decrease in the difference between involved and uninvolved FLC levels from the lowest response level, which must also be an absolute increase of at least 10 mg/dL OR• $\geq 50\%$ decrease in the level of involved FLC AND a $\geq 50\%$ decrease in the ratio of involved/uninvolved FLC from the lowest response level.
Progressive Disease (PD)	
If only measurable parameter is serum immunoglobulins free light (FLC), EITHER of the following qualify as progression:
 
• $\geq 50\%$ increase in the difference between involved and uninvolved FLC levels from the lowest response level, which must also be an absolute increase of at least 10 mg/dL OR• $\geq 50\%$ increase in the level of involved FLC AND a $\geq 50\%$ increase in the ratio of involved/uninvolved FLC from the lowest response level.

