Minimal response (MR)	
MR included participants in whom some, but not all, criteria for PR were fulfilled, providing the remaining criteria satisfied the requirements for MR. Required all of the following:
 
$\geq 25\%$ to 49% reduction in the level of serum monoclonal protein for at least two determinations six weeks apart.
 
If present, a ≥ 50 to 89% reduction in 24-hour light chain excretion, which still exceeds 200 mg/24 h, for at least two determinations six weeks apart.
 
$\geq 25\text{--}49\%$ reduction in the size of plasmacytomas (by clinical or radiographic examination) for at least six weeks.
 
No increase in size or number of lytic bone lesions (development of compression fracture does not exclude response).^c

No change (NC)	Not meeting the criteria for MR or PD.
Progressive disease (PD) (for participants not in CR)	
Requires one or more of the following:
 
$>25\%$ increase^d in the level of serum monoclonal paraprotein, which must also be an absolute increase of at least 5 g/L and confirmed on a repeat investigation.
 
$>25\%$ increase^d in 24-hour urinary light chain excretion, which must also be an absolute increase of at least 200 mg/24 h and confirmed on a repeat investigation.
 
$>25\%$ increase^d in plasma cells in a bone marrow aspirate or on trephine biopsy, which must also be an absolute increase of at least 10%.
 
Definite increase in the size of existing lytic bone lesions or soft tissue plasmacytomas.
 
Development of new bone lesions or soft tissue plasmacytomas (not including compression fracture).
 
Development of hypercalcemia (corrected serum calcium >11.5 mg/dL or 2.8 mmol/L not attributable to any other cause).

CONFIDENTIAL

This document is confidential. Do not disclose or use except as authorized.

	
Required at least one of the following:
 
Reappearance of serum or urinary paraprotein on immunofixation or routine electrophoresis confirmed by at least one follow-up and excluding oligoclonal immune reconstitution.
 
Relapse from CR
 
≥5% plasma cells in the bone marrow aspirate or biopsy.
 
Development of new lytic bone lesions or soft tissue plasmacytomas or definite increase in the size of residual bone lesions (not including compression fracture).
 
Development of hypercalcemia (corrected serum calcium >11.5 mg/dL or 2.8 mmol/L not attributable to any other cause)^e.

--	---

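### The maintenance trigger for re-adding dexamethasone uses one 0.5 g/dL rise for serum, urine and FLC; it fits serum only and is 50 times the protocol's own FLC figure

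*Combined protocol and SAP*

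**What the plan says.** Section 1.3 (Duration of Study) defines biochemical progression in maintenance as an increase of at least 25%, together with an absolute increase of at least 0.5 g/dL, "from their nadir in their serum or urine m-spike or FLC with no CRAB features attributable to MM progression". The footnote to Table 8 in section 5.1 repeats this. When it is met, "high-dose dexamethasone may be re-added to the combination at a dose of 40mg oral given on days 1, 8, and 15" of each 28-day cycle, once the overall principal investigator has been consulted. No other section gives a separate urine or FLC figure for this trigger.

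The PD criteria in section 11.2.2 set a separate threshold for each marker:

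- **Serum M-protein:** 0.5 g/dL in 11.2.2.1; 5 g/L in 11.2.2.3.
- **Urine:** 200 mg per 24 hours in 11.2.2.1. Section 11.2.2.3 likewise asks for a rise of more than 25% "in 24-hour urinary light chain excretion, which must also be an absolute increase of at least 200 mg/24 h".
- **FLC:** section 11.2.2.1 says "If serum and urine M-protein are unmeasurable, there must be an absolute increase of" 10 mg/dL in the difference between involved and uninvolved chains. The first option in 11.2.2.2 asks for a 50% rise in that difference, "which must also be an absolute increase of at least 10 mg/dL".

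**The concern.** A single g/dL figure cannot suit three markers that the protocol measures on different scales. FLC thresholds are in mg/dL, and urine is measured as 24-hour excretion rather than concentration. The wording leaves no room to read 0.5 g/dL as applying to serum alone, because the one figure governs the whole list in both places.

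The protocol expects patients who are followed by the other two markers. Section 3.1.2 states that "Free Light Chain Smoldering Myeloma patients as defined in section 2.4 are not excluded" and lists urinary light-chain excretion of 500 mg/24 hours or more as a qualifying feature. Footnote 9 to the study calendar provides for patients followed mainly by UPEP. Section 11.2.2.2 exists for patients with no measurable M-spike.

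A serum-followed patient qualifies for dexamethasone at the protocol's absolute PD figure. An FLC-followed patient must exceed that figure many times over. Some such patients could meet the definition of symptomatic myeloma in section 11.1, which ends protocol therapy under section 5.5, before they meet a trigger meant to act earlier.

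**Working it through.** The plan derives no number here, so there is nothing to reproduce. The check is a unit conversion followed by a comparison with the protocol's own PD figures.

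**Conversion.** 0.5 g/dL × 1,000 = 500 mg/dL; × 10 = 5,000 mg/L.

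| Marker | Trigger (1.3, Table 8 footnote) | PD absolute rise | Trigger ÷ PD |
|---|---|---|---|
| Serum M-protein | 0.5 g/dL | 0.5 g/dL (11.2.2.1); 5 g/L ÷ 10 = 0.5 g/dL (11.2.2.3) | 1 |
| FLC | 500 mg/dL | 10 mg/dL (11.2.2.1; first option in 11.2.2.2) | 500 ÷ 10 = 50 |
| Urine | 500 mg/dL | 200 mg/24 h (11.2.2.1, 11.2.2.3) | depends on urine volume |

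**FLC.** The PD figure applies to the involved-minus-uninvolved difference, while the trigger says only FLC. The factor of 50 compares the absolute figures as written. If the uninvolved chain is steady, a rise in the involved chain equals the rise in the difference, so the factor carries over unchanged. The second PD option in 11.2.2.2 has no absolute floor at all, which widens the gap.

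**Urine.** Excretion at the trigger = 500 mg/dL × 24-hour volume in dL. The documents give no volume, so these are assumptions:

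| Assumed volume | Rise at trigger | ÷ 200 mg/24 h |
|---|---|---|
| 0.5 L | 500 × 5 = 2,500 mg | 12.5 |
| 1 L | 500 × 10 = 5,000 mg | 25 |
| 2 L | 500 × 20 = 10,000 mg | 50 |
| 3 L | 500 × 30 = 15,000 mg | 75 |

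The two rules agree only at 200 ÷ 500 = 0.4 dL, or 40 mL a day.

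**Relation to the section 11.1 endpoint.** After a rise of 5,000 mg/L the involved chain is at least 5,000 mg/L. The involved/uninvolved ratio is then at least:

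- 5,000 ÷ 10 = 500 if the uninvolved chain is 10 mg/L;
- 5,000 ÷ 50 = 100 if it is 50 mg/L;
- 5,000 ÷ 100 = 50 if it is 100 mg/L.

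So the ratio reaches 100, a myeloma-defining event in section 11.1, whenever the uninvolved chain is at or below 50 mg/L. Section 2.4 exempts light-chain smoldering myeloma from the ratio criterion; section 11.1 does not repeat that exemption.

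**The case against.** The arithmetic is not in dispute. The case on the other side concerns how much it matters.

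- **The trigger need not equal PD.** Nothing ties it to section 11.2.2, and biochemical PD is not among the reasons for stopping therapy in section 5.5. Section 2.9.1 also notes that dexamethasone may dampen the response to nivolumab, so easier re-addition is not plainly better. This is fair, but nothing in the protocol suggests that a higher bar was intended for FLC and urine alone, and the serum figure matches PD exactly.
- **The ratio argument is weakest for the patients most affected.** Those followed only by FLC are largely light-chain smoldering patients, whom sections 2.4 and 3.2.1 exempt from the ratio criterion. The argument also needs an uninvolved chain at or below 50 mg/L, which the documents do not address. This limits the consequence, not the 50-fold mismatch.
- **Little use of the rule remains.** Accrual and nivolumab stopped with the September 2017 hold, and this version is dated 23 January 2018. Twelve 28-day cycles are 336 days, so without delays a patient who started just before the hold would finish around August 2018. Section 1.1 now adds that "Participants may elect to remain on lenalidomide/dexamethasone or lenalidomide therapy alone for disease control after discussion with the overall PI", with no biochemical threshold. This stands in part: that wording speaks of remaining on treatment, so it is only a partial route for patients already in maintenance without dexamethasone.
- **It is a drafting inconsistency, not a miscalculated result.** Agreed. The arithmetic serves only to size it.

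**Conclusion.** The concern holds, as a minor one. The 0.5 g/dL figure is right for serum M-spike, 50 times the protocol's figure for FLC, and in the wrong unit for urine. The FLC factor rests on stated figures alone, with the caveat that PD is measured on the difference between chains. The urine factor of 25 to 50 rests on an assumed 1 to 2 L a day (12.5 to 75 over 0.5 to 3 L).

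The damage is limited. The rule only permits dexamethasone after consultation, patients with a measurable serum M-spike can still qualify through it, and it defines no endpoint and does not enter the sample size or error rates. How many patients are followed only by FLC or urine is not stated.

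**What to change.** In section 1.3 and the Table 8 footnote, keep the rise of at least 25% from nadir and the absence of CRAB features, and replace the single absolute figure with those of section 11.2.2.1:

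- serum M-spike: at least 0.5 g/dL;
- urine M-protein: at least 200 mg/24 h;
- involved-minus-uninvolved FLC difference: at least 10 mg/dL.

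This aligns the absolute figures with 11.2.2.1. It does not make the trigger identical to 11.2.2.2, which asks for a 50% rise in FLC; if the sponsor wants that percentage for patients followed by FLC alone, it should be written in.

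The cost is wording in two places, with figures the protocol already contains and no new test. A few more FLC- or urine-followed patients would come up for discussion with the overall principal investigator, and some might receive more dexamethasone.
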